7.8.4 Vital Signs

For vital signs (VS) parameters, summary statistics will be presented by the visit except for Visit 2 (transfusion visit) where VS will be presented by pre, during (15-minute time intervals) and post transfusion. For post-baseline visits, summary statistics on the change from baseline will also be presented.

7.8.5 Arterial Blood Gases Evaluation (Burn patients group only)

Summary statistics on the Arterial Blood Gases test results will be presented by visit. For post-baseline visits, summary statistics on the change from baseline will also be presented. Frequency tables on the clinical interpretation of Arterial Blood Gases test results (*e.g.*, normal, abnormal but not clinically significant, abnormal, and clinically significant) will be presented by visit. For the post transfusion evaluation, the shift from baseline will also be presented.

Each Arterial Blood Gas parameter will be presented in a separate table. A list of all Arterial Blood Gas parameters (including specification of the standardised units to be used for analysis) is presented below.

Arterial Blood Gases (Burn patients group only)

pН

| pO2 kPa |
|----------------------|
| pCO2 kPa |
| HCO3 mmol/L |
| Base (excess) mmol/L |

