3.3 Clinical investigation outcomes

3.3.1 **Primary outcome**

Number of participants who experienced an adverse event (all types/grades) from transfusion up to 24 hours and 7 days (+/- 1 day) post transfusion.

3.4 Secondary Outcomes:

1. Evaluation of blood pH, pO2, pCO2, HCO3 and base (excess) before, during and after the transfusion (Burn patients group only).

LINK Medical Study ID: HEM001

- 2. Hemoglobin level before the following transfusion
- 3. Frequency of all AEs, including transfusion related AEs up to 7 days (+/- 1) post-transfusion
- 4. AEs up to 28 days after the initial transfusion, or up to subsequent transfusion episode, whichever comes first.
- 5. Frequency of all AEs, from enrollment, up to 7 days (+/- 1 day) post transfusion, through the assessment patient's diary, when applicable.
- 6. Vital signs over the course of the transfusion and up to 15 minutes post-transfusion.

4 Study Design

This is a single center clinical trial of surgical bleeding in burn patients, and chronically transfused patients with haematologic malignancies. Patients are transfused with hypoxic red blood cells manufactured with Hemanext ONE system". The patient groups are burn patients and chronically transfused patients with haematologic malignancies. Patients need to be adults \geq 18. There will be no randomization of Patient s, no blinding, and no comparator.

A first cohort of 5 patients – solely from the hematological malignancies (chronically transfused) group - will be enrolled, transfused and followed-up until their subsequent transfusion or 28 days (+/- 1 day) post-transfusion, whichever comes first. All safety related data from this initial cohort of 5 patients will be reviewed and assessed by the clinical investigation Data Monitoring Committee (DMC). Upon favourable opinion from the clinical investigation DMC, the enrolment of the remaining patients (both groups) will resume until completion.

Each patient is expected to attend 5 visits:

- 1. Visit 1 (Screening): Determine eligibility and obtain baseline data, physical examination, and safety assessments.
- 2. Visit 2 (Transfusion Day):
 - a. Pre-Transfusion: eligibility, hemoglobin, and safety assessments
 - b. Transfusion: transfusion, safety assessments, and device integrity
 - c. Post-Transfusion: safety assessments, hemoglobin, and device integrity
- 3. Visit 3 Follow-Up (24 hours post-transfusion): safety assessments and device integrity

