6.2.2 Arterial Blood Gasses

Assessment of Arterial Blood Gases (ABG) will be performed on the burn patient group only. ABG will be measured at three time points during Visit 2 (transfusion visit):

- 1. Pre-operative (pre transfusion)
- 2. Intra-operative (during transfusion)
- 3. Post operative (post transfusion)

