7.1.2 Baseline

Unless stated otherwise, the baseline value for a parameter is defined as the last non-missing value before the transfusion.

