7.1.4 Analysis Visit

An analysis visit is defined as a categorical variable used to classify values within an analysis variable into temporal or conceptual groups used for analyses.

The visits as defined in the case report form, CRF, will be used as analysis visits.

In general, data from unscheduled visits will be presented in data listings only and not included in analysis or summary tables. An exception to this is data used to confirm eligibility in association with screening where the last assessment will be considered in summaries of screening data.

LINK Medical Study ID: HEM001

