9.3 Change from Baseline

Change from baseline will be computed as the difference between a post-baseline value and the corresponding baseline value.

Percentage change from baseline will be computed as 100 times the change from baseline divided by the baseline value.

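### SAP 7.8.5 summarises arterial blood gases by visit, but all three samples fall in Visit 2, so the before/during/after outcome is not separated and no numeric change is specified by time point

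*SAP*

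**What the plan says.** SAP 6.2.2 fixes the sampling: "ABG will be measured at three time points during Visit 2 (transfusion visit"). The three points are pre-operative, intra-operative and post-operative, which the SAP equates with before, during and after transfusion. SAP 3.4 defines the matching secondary outcome, for burn patients only, as "Evaluation of blood pH, pO2, pCO2, HCO3 and base (excess) before, during and after the transfusion".

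SAP 7.8.5 sets the analysis:

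- Level of summary: "Summary statistics on the Arterial Blood Gases test results will be presented by visit". The frequency tables of clinical interpretation are also by visit.
- Numeric change: "For post-baseline visits, summary statistics on the change from baseline will also be presented".
- Categorical change: "For the post transfusion evaluation, the shift from baseline will also be presented".

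Three general rules bear on this. Under SAP 7.1.2, "the baseline value for a parameter is defined as the last non-missing value before the transfusion". Under SAP 7.1.4, "The visits as defined in the case report form, CRF, will be used as analysis visits". Under SAP 9.3, "Change from baseline will be computed as the difference between a post-baseline value and the corresponding baseline value".

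**The concern.** The outcome is a sequence of three measurements around one transfusion, so its content lies in the separate time points and the within-patient differences between them. A rule that stops at the visit does not reach that level, because all the measurements belong to one visit.

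The study has no hypothesis and only descriptive statistics are planned, so the choice of summary rows is in effect the whole analysis of this outcome. Arterial blood gases are also the only secondary objective specific to burn patients. SAP 8.1 puts this outcome in the place of the haemoglobin increment corrected for blood volume and dose. If the tables are programmed as written, the report may not show what the outcome promises. If the programmer decides how to split the rows, that choice is made outside the plan.

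**Working it through.** The plan gives no figure to reproduce, and no power or error rate is involved. The check counts samples per analysis visit and then compares the rule with its neighbours.

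**Inputs.** Burn patients: 10 (SAP 5.1). Samples per patient: 3, all in Visit 2 (SAP 6.2.2). Parameters: 5, namely pH, pO2, pCO2, HCO3 and base excess (SAP 7.8.5). Visits after Visit 2: 3, namely Visits 3, 4 and 5 (SAP 4).

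**Step 1: what a by-visit row holds.** Analysis visits carrying a planned blood gas = 1. Values under that label, per parameter, with complete sampling = 3 x 10 = 30, with three correlated values from each patient. The interpretation tables show the difficulty in another way. SAP 7.1.1 uses the number of patients in the analysis set as the percentage denominator. If every result were counted in a single Visit 2 row, up to 30 classified results would sit over 10 patients, and the categories would sum to 30/10 = 300%. The literal rule therefore needs a further decision that the SAP does not state.

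**Step 2: what the numeric-change sentence acts on.** Baseline is the last value before transfusion, which here is the pre-operative sample, itself in Visit 2. Later visits with a planned blood gas = 0 of 3. Under SAP 7.1.4, results from unscheduled visits generally go to listings only, so an extra sample would not fill the gap. Read strictly, the sentence has no data.

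**Step 3: what survives.** The post-transfusion shift from baseline compares one post-operative with one pre-operative category per patient, n up to 10 for each parameter. The intra-operative sample enters no stated comparison with baseline.

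**Step 4: comparison with neighbouring sections.**

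| Measurement | When taken | Stated level of summary |
|---|---|---|
| Haemoglobin (SAP 7.8.3) | Visit 2 twice, Visit 5 | summary statistics by visit and also by time point |
| Vital signs (SAP 7.8.4) | Visits 1 and 2 | Visit 2 split into pre, during and post |
| Blood gases (SAP 7.8.5) | Visit 2 only, three times | by visit only |

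The measurement most dependent on a split within Visit 2 is the one without it.

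**Step 5: after the correction.** Per parameter, 3 time-point summaries and 2 paired changes (intra minus pre, post minus pre), each with n up to 10. Over 5 parameters, that is 5 x 3 = 15 summaries and 5 x 2 = 10 change summaries.

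**The case against.** The best defence is that the intent is clear and the wording loose. Several points support it.

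- *The shift table.* It requires pre- and post-transfusion values to be kept apart. This stands. A reader might infer from the by-visit rule that no change from baseline is planned at all; the shift sentence in the same section rules that out.
- *Pooling.* A reader might also infer that the SAP intends to average the three samples. No section says so. Pooling is only what the words produce if followed literally, and SAP 6.2.2 and 3.4 both name the three points.
- *House style.* The sentence on post-baseline visits also appears for vital signs, which are taken only at Visits 1 and 2 and so have no later visit either. There it can only sensibly mean points within Visit 2. This stands and makes a sensible reading of 7.8.5 likely. But the vital-signs section states its split of Visit 2, so its reader is told what to do.
- *Definition of change.* SAP 9.3 defines change on values, not visits. That settles how to compute a change; 7.8.5 still decides where one is reported.
- *Unseen documents.* Analysis visits follow the CRF, and mock tables are in the Data Display Plan. Either could carry the split, and neither is available here. However, SAP 4 and the burn flow chart in Appendix B treat pre-, during- and post-transfusion as parts of a single Visit 2.
- *Listings.* Individual data will be listed, so no measurement is lost.

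Two further arguments might be added and should not be. One is that pO2 cannot be interpreted without inspired oxygen; the documents give no information or figure on this. The other is that the burn flow charts have no blood-gas row; that is clerical, since SAP 6.2.2 gives the timing.

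**Conclusion.** The concern holds as a conflict between a stated rule and the outcome it serves. SAP 7.8.5 specifies neither summaries and interpretation tables by time point within Visit 2, nor numeric change by time point, nor any intra-operative comparison with baseline. The categorical pre-to-post shift is planned and remains valid.

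The importance is modest: a descriptive secondary outcome in 10 burn patients, with no effect on the primary outcome. The figures of 30 values per visit label and n up to 10 assume that all 10 patients are sampled at all three points. The protocol collects blood gases only when applicable, so the real numbers may be smaller. The conclusion also assumes that the CRF numbers its visits as the flow charts do. If the CRF or the Data Display Plan already separates the three points, only the SAP wording is at fault.

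**What to change.** In SAP 7.8.5:

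1. Replace by visit with by time point (pre-, intra-, post-operative), for both the summary statistics and the clinical-interpretation tables.
2. Replace post-baseline visits with post-baseline time points, and state that change is the paired within-patient difference from the pre-operative value, with the number of pairs shown (up to 10 per parameter).
3. Keep the existing post-transfusion shift table.

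Check that the mock tables in the Data Display Plan use the same rows. The cost is a wording change in one SAP section and, if needed, matching table shells. No extra sampling, CRF field or patient contact is required.

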7.8.6 Hematology and Blood chemistry

Hematology and blood chemistry data is exclusively gathered as a backup for AE findings and will not be incorporated into the analysis. Consequently, no summary tables for hematology or blood chemistry test results will be generated, except for hemoglobin as described above. The presentation of test results will be limited to listings only.

7.8.7 Physical Examination

For all body systems examined, frequency tables on the investigator's assessment will be presented by visit. For post-baseline visits, the shift from baseline will also be presented.

8 Changes to Planned Analysis

8.1 Exclusion and modification of secondary objectives

Two of the secondary objectives have been modified or excluded

- "Assessment of AEs occurrence up to 7 days (+/- 1 day) post transfusion, in comparison with historical control (including but not limited to infection, deep vein thrombosis, acute respiratory distress syndrome, transfusion-related acute lung injury, transfusion associated circulatory overload, anaphylactic shock, acute haemolytic transfusion reaction)" Outcome 1 has been revised to "Assessment of AEs occurrence up to 7 days (+/- 1 day) post transfusion (including but not limited to infection, deep vein thrombosis, acute respiratory distress syndrome, transfusion-related acute lung injury, transfusion (including but not limited to infection, deep vein thrombosis, acute respiratory distress syndrome, transfusion-related acute lung injury, transfusion associated circulatory overload, anaphylactic shock, acute haemolytic transfusion reaction)". The reason for the change is that data on historical control is not available.
- "Hemoglobin increment from transfusion corrected for patient blood volume and hemoglobin dose" Has been replaced with "Evaluation of blood pH, pO2, pCO2, HCO3 and base (excess) before, during and after the transfusion."

8.2 Allowing for time intervals in vital signs (VS) measurements.

Instead of presenting VS measurements every 15 minutes during and after the transfusion, they will be presented within 15-minute time intervals. If two measurements fall within the same interval, the measurement closest to the intended assessment time will be used.

9 Derived Variables

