11. CLINICAL INVESTIGATION ASSESSMENTS

The following information will be collected, from enrollment throughout end of study visit, when applicable:

- 1. Patient consent
- 2. Inclusion/Exclusion criteria
- 3. Demographics
- 4. Medical history
- 5. Physical examination
- 6. Pregnancy test (if applicable)
- 7. Height
- 8. Weight
- 9. RBC unit weight and volume
- 10. Age of the RCC unit at the time of the transfusion
- 11. Hemoglobin measurement maximum 4 hours before the transfusion and at minimum 15 minutes before transfusion
- 12. Hemoglobin measurement 15 to 60 minutes after transfusion
- 13. Blood pressure every 15 minutes during the transfusion and until 15 minutes after the end of the transfusion
- 14. Heart rate every 15 minutes during the transfusion and until 15 minutes after the end of the transfusion
- 15. Body temperature every 15 minutes during the transfusion and until 15 minutes after the end of the transfusion
- 16. Respiratory rate every 15 minutes during the transfusion and until 15 minutes after the end of the transfusion
- 17. Oxygen saturation every 15 minutes and until 15 minutes after the end of the transfusion
- Patient diary for collection of concomittant medications and changes in health status from enrollment up to their following transfusion or 28 days (+/- 1 day) posttransfusion whichever comes first
- 19. Routine laboratory analyses, including blood gases when applicable.

11.1 Clinical investigation flow chart(s) / table of clinical investigation procedures and assessments

Investigation Periods	Screening & Enrollment Visit	Pre- Transfusi on	Transfusion	Post- Transfusion	Follow Up 1	Follow-up 2	Follow-up 3
Visit	1	2	2	2	3	4	5
Time (hour, day, week)	D0	D1	D1	D1	D2 (≤ 24h)	D7 (+/- 1 day)	Day of subsequent transfusion or D28, whichever comes 1 st
In- /Exclusion Criteria	x	x					
Patient Information							
Patient consent (ICF)	x						
Demographics	x						
Medical History	x						
Concomitant Medications	x	x	x	x	x	x	x
Physical Examination	x						x
Pregnancy Test	x						
Height	х						
Weight	x						
RBC Unit Weight		x					
Patient Hemoglobin		x		x			x
Blood Pressure	x	x	x	x			
Heart Rate	x	x	x	x			
Body Temperature	x	x	x	x			
Respiratory Rate	x	x	x	x			
Oxygen Saturation	x	x	x	x			
Transfusion			x				
Adverse Events, Adverse device effects	x	x	x	x	x	x	x
Review Device Integrity		x	x	x			
Patient Diary	x	x	x	x	X	x	

11.1.1 Hematogical Malignancies Group:

11.1.2 Burn patients Group:

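### Change in arterial pO2 across pre-, intra- and post-operative samples cannot be interpreted without inspired oxygen, which neither document collects

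*SAP*

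**What the plan says.** - **Outcome.** SAP 8.1 substitutes "Evaluation of blood pH, pO2, pCO2, HCO3 and base (excess) before, during and after the transfusion" for the haemoglobin increment corrected for blood volume and haemoglobin dose. SAP 3.4 lists it first among the secondary outcomes, for burn patients only. Blood gases were already a burn-group objective in Protocol 6.3.
- **Timing.** SAP 6.2.2 states: "ABG will be measured at three time points during Visit 2 (transfusion visit"). It equates the transfusion stages with the surgical ones; the second time point, for example, is "Intra-operative (during transfusion").
- **Baseline.** SAP 7.1.2 takes the last available value before the transfusion, which for gases is the pre-operative sample.
- **Summaries.** SAP 7.8.5 plans descriptive statistics and a clinical-interpretation table by visit, plus a shift from baseline after transfusion. It adds: "For post-baseline visits, summary statistics on the change from baseline will also be presented".
- **Variables.** The same section says: "A list of all Arterial Blood Gas parameters (including specification of the standardised units to be used for analysis) is presented below". The list contains pH, pO2, pCO2, HCO3 and base excess.
- **Data collection.** Protocol 11 has only "Routine laboratory analyses, including blood gases when applicable". The visit schedules in both documents have no blood gas row.
- **Comparator.** Protocol 5.6 says there is none.

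**The concern.** Arterial pO2 depends directly on the oxygen fraction the patient breathes. If that fraction differs between the pre-operative sample and a later one, pO2 moves whatever the transfused cells or the lungs are doing. Under SAP 6.2.2 every change from baseline spans surgery, a period over which inspired oxygen may change. Without FiO2 the reader cannot separate the two sources, and with no control group nothing cancels a peri-operative shift. If ventilation is controlled, pCO2 is partly set from outside the patient, and pH moves with it.

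What is at stake is the reading of one secondary outcome. Protocol 6.3 names acute respiratory distress syndrome, TRALI and TACO among the events of interest. A pO2 summary without inspired oxygen gives little information on gas exchange, and its change says nothing reliable about the transfusion.

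**Working it through.** The plan gives no expected pO2, standard deviation or FiO2, so there is no figure of its own to reproduce. The check has three parts.

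**1. Is inspired oxygen collected anywhere?**

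- SAP 7.8.5: its list, described as complete, has five gas parameters and neither FiO2 nor a pO2/FiO2 ratio. This is the informative place.
- Protocol 11 names no gas components, and the schedules have no gas row, so their silence on FiO2 adds little.
- SAP 9 (derived variables): no ratio or adjustment.
- Oxygen saturation and concomitant medications are collected, but neither is tied to a gas sample and neither replaces FiO2.

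**2. How far could FiO2 alone move pO2?**

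Alveolar gas equation in kPa:

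PAO2 = FiO2 × (101.3 − 6.3) − PaCO2 / 0.8

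All inputs are assumptions: barometric pressure 101.3, water vapour 6.3, PaCO2 5.3, respiratory quotient 0.8. The last term is 5.3 / 0.8 = 6.625. The arterial change is taken as 0.5 to 0.75 of the alveolar change, also an assumption.

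| FiO2 | PAO2 (kPa) | Change from 0.21 | Approximate arterial change |
|---|---|---|---|
| 0.21 | 19.95 − 6.625 = 13.3 | 0 | 0 |
| 0.25 | 23.75 − 6.625 = 17.1 | 3.8 | 1.9 to 2.9 |
| 0.30 | 28.5 − 6.625 = 21.9 | 8.6 | 4.3 to 6.4 |
| 0.50 | 47.5 − 6.625 = 40.9 | 27.6 | 13.8 to 20.7 |

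Two comparisons give scale:

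- A PaCO2 shift from 4.5 to 6.0 kPa moves alveolar pO2 by 1.5 / 0.8 = 1.9 kPa.
- With n = 10, the 95% half-width of a mean change is t(0.975; 9) × SD / √10. For an assumed SD of 1 to 5 kPa, that is 0.7 to 3.6 kPa.

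On these assumptions, a rise from 0.21 to 0.30 in all patients would exceed that half-width, whereas an unchanged FiO2 adds nothing.

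The opposite case also matters. A pO2 of 13 kPa gives a ratio of 13 / 0.21 = 62 kPa at FiO2 0.21 and 13 / 0.50 = 26 kPa at FiO2 0.50. A numerical summary of raw pO2 shows these as the same value.

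**3. Does the layout separate the three samples?**

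SAP 7.8.5 presents gases by visit and change for post-baseline visits, but SAP 6.2.2 puts all three samples in Visit 2. Read literally, the by-visit layout does not distinguish them. SAP 7.8.3, on haemoglobin, does specify both visit and time point.

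**The case against.** A reader might go further and infer that the pO2 change mainly shows oxygen given under anaesthesia. The documents do not support that: neither mentions anaesthesia, ventilation or supplemental oxygen, and SAP 6.2.2 says only pre-, intra- and post-operative. FiO2 may be similar at all three times in some patients, and the effect is then zero. The larger figures above assume a baseline on air and are alveolar.

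A reader might also infer that a rise in pO2 would be presented as a benefit. Protocol 5.7.1 does list better oxygen delivery as a potential benefit. However, Protocol 5.1.6 argues it through 2,3-DPG and the dissociation curve, not through higher arterial pO2. The gases sit under safety evaluation in SAP 7.8, Protocol 13.1 has no hypothesis, and Protocol 13.4.3 limits secondary endpoints to description.

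A third inference is that a lung reaction could be hidden and classed as normal. The table in SAP 7.8.5 records clinical interpretation, which may allow for delivered oxygen, although the SAP does not require it. Detection does not rest on that table. Adverse events are monitored directly at the transfusion (Protocol 11.2.1), respiratory rate and saturation are taken every 15 minutes (Protocol 11), and the data monitoring committee reviews all adverse events (Protocol 3.6).

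Finally, the case report form and Data Display Plan are not among the documents, so FiO2 might be captured there. FiO2 by mask or nasal oxygen is also only an estimate, which weakens a ratio built on it. These objections limit the size and reach of the point. They do not make the numerical pO2 change interpretable as planned.

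**Conclusion.** The concern holds in a limited form. As written, SAP 7.8.5 reports a pO2 change and shift that are open to confounding by inspired oxygen and cannot be attributed to the transfusion or read as lung function. The same applies to pCO2 and pH if ventilation is controlled; HCO3 and base excess are not challenged here.

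The direction and size of any distortion are unknown, because they depend on FiO2 values that the documents do not give. The illustrative alveolar range runs from 0 to about 28 kPa for FiO2 between 0.21 and 0.50.

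The consequence is confined to a secondary, descriptive safety table in a planned 10 burn patients. The primary outcome and the sample size are unaffected, and no error rate is involved. It is worth correcting because the remedy is cheap, not because the trial's main conclusion depends on it.

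**What to change.** 1. For each blood gas, transcribe FiO2 and whether the patient was ventilated or breathing spontaneously, from existing records. Flag FiO2 as estimated where oxygen was given by mask or nasal route.
2. In SAP 7.8.5, present gases by time point (pre-, intra- and post-operative) instead of by visit. Add pO2/FiO2 as the variable used for change from baseline.
3. Keep raw pO2 as descriptive values or in the listing, with a footnote that its change is not interpretable without FiO2.
4. Flag pCO2 and pH by ventilation status.
5. If FiO2 was not recorded, list raw pO2 and omit its change and shift summaries.

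The cost is two transcribed fields and one derived variable. With 10 patients and three samples each, that is at most 30 samples and 60 entries. No sample or procedure is added, so this is consistent with Protocol 11.2, which rules out assessments beyond standard care. The drawback is that pO2/FiO2 is only as good as the recorded FiO2, hence the flag for estimates.
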